### **9.2.2.8 Adverse events related to COVID-19 vaccination**

The TEAE related to COVID-19 vaccination, which will be captured on the CRF page, will be categorized and presented by SOC and PT in a manner similar to that described in the Section 9.2.2.1.

## **9.3 Other safety variables**

Unless otherwise indicated baseline is defined as the last non-missing data collected prior to the first dose of study medication (including Placebo and BRV) in core study. Core study is defined as the first study a study participant was enrolled in.

### **9.3.1 Laboratory measurements**

#### **9.3.1.1 Hematology, biochemistry and urinalysis parameters**

All summaries will be based on the standard international units.

The observed values and change from baseline will be presented descriptively for hematology and biochemistry assessments with numeric values by study group for each scheduled visit (not including EV) and for Last Value. Change from baseline will be presented for each scheduled post-baseline visit and Last Value. Last Value is the last available assessment during treatment with BRV.

For the qualitative urinalysis parameters, the number and percentage of subjects with each response category will be summarized for Baseline, scheduled visits and Last Value.

Possibly clinically significant treatment-emergent (PCST) abnormalities for laboratory values will be summarized by visit and at Last Value as stated above. The PCST abnormality will also be summarized with shift tables of post-baseline results versus baseline results. Details of PCST criteria are available in Section 12.1.

Urine pregnancy test results will not be summarized but will be provided in a subject data listing.

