## 12 APPENDICES

### 12.1 PCST criteria

#### 12.1.1 Laboratory assessments - PCST

The following criteria will be applied in the determination of PCST laboratory assessment values.

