##### 12.1.1.1 Hematology

**Table 2: Hematology PCST criteria**

PARAMETER	AGE RANGE	UNIT (standard)	ABNORMALITY CRITERIA (standard)
Hematocrit	<2y	%	≤27, >45
	2y - <18y		≤29, >47
	≥18y		≤85% of LLN, ≥115% of ULN
Hemoglobin	<2y	g/L	≤90, >150
	2y - <18y		≤95, >160
	≥18y		≤85% of LLN, ≥115% of ULN
WBC/Leukocytes	<12y	G/L	<3.5, >15.0
	≥12y		<3.0, >12.0
Neutrophils Absolute	>1m	G/L	<1.5
Lymphocytes	<6m	%	≤30.0
	6m - <6y		≤22.0
	6y - <18y		≤12.0, ≥80.0
	≥18y		≤10.0, ≥80.0
Basophils	>1m	%	≥3.0
Eosinophils	>1m	%	≥10.0

PARAMETER	AGE RANGE	UNIT (standard)	ABNORMALITY CRITERIA (standard)
Monocytes	>1m	%	≥20.0
Platelets	>1m	G/L	≤100, >600
RBC/ Erythrocytes	<2y	T/L	<3.0
	≥2y		<3.5

Abbreviations: F=female; M=male; m=month; PCST=possibly clinically significant treatment-emergent; y=year. A month is defined as 30 days; a year is defined as 365.25 days.

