### 12.1.1.2 Blood chemistry

**Table 3: Chemistry PCST criteria**

PARAMETER	AGE RANGE	UNIT (standard)	ABNORMALITY CRITERIA (standard)
AST (SGOT)	<14y	U/L	>180
	≥14y		>144
ALT (SGPT)	1y - <18y	U/L	>90
	≥18y		>123
Alkaline Phosphatase	<4y	U/L	>690
	4y - <10y		>834
	10y - <18y		>1174
	≥18y		>432 (F), >933 (M)
GGT	<6m	U/L	>522
	6m - <1y		>279
	1y - <13y		>66

PARAMETER	AGE RANGE	UNIT (standard)	ABNORMALITY CRITERIA (standard)
	13y - <18y		>126
	≥18y		>255
Total Bilirubin	>1m	umol/L	≥25.656
Total Protein	2m-<1y	g/L	<30, >100
	≥1y		<43, >100
Albumin	<1y	g/L	<16, >60
	≥1y		<24, >70
BUN	<1y	mmol/L	>7.497
	≥1y		>10.71
Urea	<1y	mmol/L	>7.014
	≥1y		>10.02
Creatinine	1y - <10y	umol/L	>79.56
	10y - <16y		>123.76
	≥16y		>141.44
Creatinine Clearance *	All	mL/s	<1.169
Calcium	<1y	mmol/L	<1.725, >3.05
	1y - <18y		<1.85, >2.925
	≥18y		≤1.975, ≥2.775
Phosphorous	<1y	mmol/L	<0.5814, >2.6486
	≥1y		<0.5814, >2.3902
Potassium	<1y	mmol/L	<3.0, >6.5

PARAMETER	AGE RANGE	UNIT (standard)	ABNORMALITY CRITERIA (standard)
	≥1y		<3.0, >5.8
Sodium	>1m	mmol/L	≤130, ≥150
Glucose	>1m	mmol/L	<2.775, >9.99
Total Cholesterol	1y - <18y	mmol/L	>6.475
	≥18y		>7.77
LDL (calculated)	1y - <18y	mmol/L	>3.626
	≥18y		>5.18
HDL	≤2y	mmol/L	<0.259
	>2y		<0.518
Triglycerides	<1y	mmol/L	>8.475
	≥1y		>2.825
Uric Acid	<1y	umol/L	>457.996
	1y - <13y		>386.62
	13y - <18y		>511.528
	≥18y		>404.464 (F), >571.008 (M)
Thyroxine (T4)	<1y	nmol/L	≤55.3453, ≥236.8264
	≥1y		≤48.9098, ≥173.7585
Globulin	<1y	g/L	<10, >38
	≥1y		<12, >44

Abbreviations: ALT= alanine aminotransferase; AST = aspartate aminotransferase; BUN = blood urea nitrogen; Cr CL=creatinine clearance; dL = deciliter; F=female; GGT: gamma-glutamyltransferase; HDL = high density lipoprotein; LDL = low density lipoprotein; L = liter; M=male; m = month (a month is defined

as 30 days) mg = milligram; mmol = millimoles; µg = microgram; PCST=possibly clinically significant treatment-emergent; U = unit; ULN = upper limit of normal; y = years (a year is defined as 365.25 days)

\* Schwartz equation (patients <12): Cr Cl ml/min = [Height (cm) \* 0.55] / serum creatinine; Cockcroft equation (patients >12): Male: Cr Cl ml/min = [(140-age) × body weight (kg)] / (72 × serum creatinine); Female: Cr Cl ml/min = [(140-age) × body weight (kg)] / (72 × serum creatinine)] × 0.85

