### 12.1.1.3 Urinalysis

Qualitative urine parameters are generally reported by a descriptive score, which differs among laboratories. For data analysis purpose, a 4-point scale is used. Five-point, 6-point, or 7-point scales will be collapsed into a 4-point scale first. A value is considered possibly clinically significant treatment-emergent abnormal if an upward shift of at least 2 degrees from the baseline occurs under investigational treatment. To collapse the results in a 5-point scale into a 4-point scale, the lowest 2 positive results will be combined (see example below). For results reported with a scale of more than 5-point, please consult your study physician for how to collapse into 4-point scale.

Original 5-point Scale	4-point Scale
Negative/None	Negative/None
Trace/Rare/Mild/A Few	Trace/1+/Rare/Mild/A Few
1+	
2+/Mod	2+/Mod
3+/Sev	3+/Sev

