**Table 5: Vital sign PCST criteria**

PARAMETER	AGE RANGE	ABNORMALITY CRITERIA
Pulse Rate (beats/minute)	<6m	<100, >180
	6m - <3y	<90, >150
	3y - <12y	<60, >130
	12y - <17y	<50, >120
	≥17y	<50 and a decrease from Baseline of ≥15, >120 and an increase from Baseline of ≥15
Systolic Blood Pressure (mmHg)	<6m	<60, >100
	6m - <3y	<70, >120
	3y - <12y	<80, >140
	12y - <17y	<90, >160
	≥17y	≤ 90 and a decrease from Baseline of ≥20, ≥ 180 and an increase from Baseline of ≥20
Diastolic Blood Pressure (mmHg)	<6m	<40, >65

PARAMETER	AGE RANGE	ABNORMALITY CRITERIA
	6m - <3y	<45, >75
	3y - <12y	<50, >80
	12y - <17y	<50, >105
	≥17y	<50 and a decrease from Baseline of ≥15, >105 and an increase from Baseline of ≥ 15
Respiratory Rate (breaths/minute)	<6m	<25, >55
	6m - <3y	<20, >45
	3y - <12y	<15, >35
	≥12y	<10, >25
Temperature	>1m	>101°F (38.3°C)
Body Weight	1m - <17y	<3% or 97% of the normal body weight growth curve ranges based on gender and the age of subject on date of weight assessment a
	≥17y	≥ 10% change from Baseline (an increase or a decrease) a

Abbreviations: m = month, y = year. A month is defined as 30 days; a year is defined as 365.25 days.

a source: <http://www.cdc.gov/growthcharts/>: Once the subject reaches 17 years of age use the body curve criteria of a 17-year-old regardless of their age in the study.

The following table is used to judge PCST regarding body weight.

Body weight (kg) at the 3 and 97 percentiles of the distribution at each age in Japanese children

Age (years-months)		16-0	16-1	16-2	16-3	16-4	16-5	16-6	16-7	16-8	16-9	16-10	16-11	17-0
Male	3%	45.66	45.89	46.11	46.33	46.53	46.73	46.93	47.11	47.29	47.47	47.64	47.80	47.97
	97%	83.83	84.08	84.32	84.57	84.82	85.07	85.31	85.56	85.79	86.02	86.24	86.45	86.64
Female	3%	41.04	41.11	41.18	41.25	41.31	41.37	41.43	41.49	41.55	41.60	41.66	41.71	41.76
	97%	69.91	69.98	70.05	70.12	70.19	70.25	70.31	70.36	70.41	70.46	70.51	70.55	70.59

Source: The Japanese Society for Pediatric Endocrinology: [homepage on the Internet]. Available from: <http://jspe.umin.jp/pdf/fuhyo2.pdf>

This document cannot be used to support any marketing application and any extensions or variations thereof.  
PUBLIC COPY

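### Haematology and chemistry PCST criteria carry no baseline condition, so the by-visit and Last Value tables count unchanged pre-BRV abnormalities as treatment-emergent

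*SAP*

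**What the plan says.** SAP 9.3.1.1 plans three displays of laboratory PCST abnormalities. Two are counts: "Possibly clinically significant treatment-emergent (PCST) abnormalities for laboratory values will be summarized by visit and at Last Value". The third follows in the next sentence: "The PCST abnormality will also be summarized with shift tables of post-baseline results versus baseline results".

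SAP 12.1.1 settles what counts as PCST: "The following criteria will be applied in the determination of PCST laboratory assessment values". Table 2 (haematology) and Table 3 (chemistry) then list limits by age. Most are fixed cut-offs. Adult hematocrit and hemoglobin are set against the reference range, "≤85% of LLN, ≥115% of ULN". Neither table, nor the text above it, refers to the subject's own baseline.

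Two neighbouring rules do refer to it. For urinalysis (SAP 12.1.1.3): "A value is considered possibly clinically significant treatment-emergent abnormal if an upward shift of at least 2 degrees from the baseline occurs under investigational treatment". For pulse at 17 years and over (Table 5), the low criterion is "<50 and a decrease from Baseline of ≥15". Blood pressure at that age is built the same way, and adult weight is purely a change from Baseline.

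Protocol 12.4 uses the same treatment-emergent label for laboratory abnormalities without defining it. SAP 9.3 places Baseline before the first placebo or BRV dose in the core study.

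**The concern.** Treatment-emergent should mean that the abnormality appeared or worsened after treatment began. Under Tables 2 and 3 it means only that the value is beyond a limit on the day. A stable abnormality that predates BRV enters the by-visit and Last Value counts exactly as a new one does.

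The study has no control group and tests no hypothesis, so readers will take these counts at face value. Laboratory tests are a named safety variable in a study whose primary objective is long-term safety. A count that mixes old and new abnormalities under a label meaning new overstates what arose on BRV. It also uses the label differently from the urinalysis results in the same section.

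**Working it through.** The documents state no PCST rate, so there is no plan figure to reproduce. The check has four parts.

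**1. Is there a baseline condition?**

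| Parameter group | Source | Baseline condition |
|---|---|---|
| Haematology | SAP Table 2 | None (fixed, or relative to LLN/ULN) |
| Chemistry | SAP Table 3 | None |
| Urinalysis | SAP 12.1.1.3 | Upward shift of at least 2 degrees |
| Pulse, blood pressure, age 17 and over | SAP Table 5 | Limit plus change from Baseline |
| Weight, age 17 and over | SAP Table 5 | Change of at least 10% from Baseline |
| Pulse, blood pressure, age 12 to under 17 | SAP Table 5 | None |

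The shift table confirms the reading. Tabulating PCST status at baseline against post-baseline makes sense only if the limit can already be met at baseline.

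**2. Can an ordinary, unchanged value meet a limit?** Creatinine clearance serves as the example.

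- Limit in Table 3: below 1.169 mL/s at all ages. 1.169 × 60 = 70.1 mL/min.
- Formula in the Table 3 footnote: "Male: Cr Cl ml/min = [(140-age) × body weight (kg)] / (72 × serum creatinine"), multiplied by 0.85 for women. Creatinine is assumed to be in mg/dL; the footnote gives no unit.
- Woman, 60 years, 50 kg, creatinine 0.7: (80 × 50)/(72 × 0.7) × 0.85 = 67.5 mL/min.
- Man, 60 years, 60 kg, creatinine 1.0: (80 × 60)/(72 × 1.0) = 66.7 mL/min.

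Both are below 70.1. Both creatinine values are well under the SAP's own creatinine limit of 141.44 umol/L (141.44/88.4 = 1.6 mg/dL). If nothing changes, each subject is flagged at every full laboratory visit and at Last Value.

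No numeric entry limit screens clearance. The numeric laboratory limits in Protocol 6.1.5, 6.1.6 and 6.2.2 cover ALT, AST, ALP and total bilirubin only.

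**3. How far could this move a table?** This is an illustration for one parameter with all N = 217 planned subjects assessed. Let p be the proportion beyond the limit before BRV, assumed to persist, and q the new incidence among the rest. Neither is in the documents.

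Count = N·p + N·(1 − p)·q, and pre-existing share = N·p / count.

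| p | q | Count as written | New cases only | Pre-existing share |
|---|---|---|---|---|
| 1% | 5% | 12.9 (6.0%) | 10.7 | 17% |
| 1% | 2% | 6.5 (3.0%) | 4.3 | 34% |
| 5% | 2% | 15.0 (6.9%) | 4.1 | 72% |
| 10% | 2% | 25.6 (11.8%) | 3.9 | 85% |
| 10% | 1% | 23.7 (10.9%) | 2.0 | 92% |

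For the third row: 217 × 0.05 = 10.85; 217 × 0.95 × 0.02 = 4.12; total 15.0; 10.85/15.0 = 72%.

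**4. Do the shift tables close the gap?** They place a subject abnormal at both times in the abnormal-to-abnormal cell, so that subject is not shown as new. One group escapes. For a subject randomized to placebo in EP0083, Baseline precedes placebo, so an abnormality that arose on placebo appears as a new shift. The Entry Visit, which could reveal it, is left out of the by-visit summaries of observed values and change.

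**The case against.** The strongest reply is that the plan already separates old from new: the shift tables apply the same limits at Baseline, and numeric parameters also get change from baseline at each post-baseline visit. That stands for the plan as a whole. A reader might infer that emergence cannot be recovered from the planned output; the shift tables show otherwise. They do not alter the two tables that carry the wrong count, and SAP 9.3.1.1 does not say which post-baseline result they use.

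Other stronger readings also fail:

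- *The primary safety analysis is compromised.* It is not. The primary variable is TEAEs, defined by onset date in SAP 9.2.1; PCST does not enter it.
- *Renal function is unscreened at entry.* It has no numeric limit, but Protocol 6.1.4 and 6.2.2 exclude laboratory values that may affect safety, and 6.1.6 adds investigator-judgement exclusions for direct enrollers.
- *Liver tests are equally exposed.* The entry exclusion above 2 × ULN keeps adult PCST values out at the entry assessment if ULN is at most 61.5 U/L for ALT (123/2), 72 for AST (144/2), and 216 (432/2, female) or 466.5 (933/2, male) for ALP. ULNs are not in the documents. For bilirubin, an eligible subject with known Gilbert's syndrome can reach the 25.656 umol/L limit only if ULN exceeds 25.656/1.5 = 17.1 umol/L, also an assumption. The point does not rest on it.
- *Haematology and chemistry depart from one uniform definition.* Table 5 itself uses fixed pulse and blood pressure limits below 17 years, and 16-year-olds are eligible.

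Two further cautions stand. Protocol 10.2 has the central laboratory calculate clearance by its current methods, so reported values may differ from the worked examples. A baseline condition also has a price: a subject already beyond a limit who worsens on BRV leaves the count.

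**Conclusion.** The point holds for the by-visit and Last Value PCST tables for haematology and chemistry. As written, they count unchanged pre-BRV abnormalities as treatment-emergent. This is a stated rule that gives the wrong count for its label, not a missing detail. It should be corrected, but it concerns a descriptive display of secondary safety variables.

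The absence of a baseline condition rests on the SAP text alone. The clearance examples assume creatinine in mg/dL and use of the table's formula. The 17–92% range depends entirely on assumed p and q, and on abnormalities persisting; it shows the possible scale, not an estimate. The placebo-rollover gap follows from the Baseline definition in SAP 9.3.

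**What to change.** Add to SAP 12.1.1: a Table 2 or Table 3 value counts as PCST only if the limit is met on BRV and was not met at the last value before the subject's first BRV dose. The denominator at each visit is the assessed subjects who did not meet the limit at that earlier time.

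Name the pre-BRV value for each group. For EP0083 placebo rollovers it is the Entry Visit value. That assumes no BRV was given in the EP0083 Transition Period, which these documents do not describe; otherwise an earlier value is needed. For direct enrollers it is the existing Baseline. Any N01379 subject who received placebo in N01358 needs the same check.

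Show subjects already abnormal before BRV in the shift table and list them, so that worsening stays visible even though they leave the PCST count.

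The cost is one sentence, a derived flag and a changed denominator, using data already collected. Protocol 12.4 leaves the term undefined for laboratory values, so it does not conflict. If the sponsor prefers to keep all abnormal values in the count, the minimum change is to drop treatment-emergent from the titles of the by-visit and Last Value tables and rely on the shift tables for emergence. That alternative leaves the placebo-rollover gap open.

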10.2.1 Evaluation of PDILI

The PDILI IMP discontinuation criteria for this study are provided in Section 6.3.1, with the accompanying required follow-up investigation and monitoring detailed below. All PDILI events must be reported as an AE and reported to the study site and sponsor within 24 hours of learning of their occurrence. Any PDILI event that meets the criterion for potential Hy's Law must be reported as an AE of special interest (see Section 10.1.1.3), and, if applicable, also reported as an SAE (see Section 10.1.1.2).

Evaluation of PDILI consists of the diagnostic testing and continued monitoring included in Table 10–2 (specific tests dependent on laboratory results and corresponding symptoms) and consultation with a local hepatologist (if applicable; discussed in Section 10.2.1.1). The local hepatologist is the expert usually consulted by the treating physician for assessment and management of potential hepatic disease. This would usually be a hepatologist, but may be a gastroenterologist. Additional investigation and monitoring may be required and adapted based on the diagnosis after the cause of the liver injury/abnormality is confirmed (details in Section 10.2.1.4).

The results of all monitoring, including laboratory testing and other testing, should be made available to the study site and sponsor.

All initial tests resulting in abnormal hepatic laboratory values need to be repeated, but appropriate medical action must not be delayed waiting for the repeat result.

If tests are done locally for more rapid results, a concurrent sample should also be sent to the central laboratory whenever possible. Medical care decisions are to be made initially using the most rapidly available results and a conservative approach must be taken if the results from the 2 laboratory tests are significantly different. Data from the local and central laboratory are to be recorded on the applicable eCRF pages.

When IMP is discontinued, all concomitant medications and herbal supplements that are not medically necessary should also be discontinued. In these cases, the Investigator should also consider dose reduction for medically necessary concomitant medication and consider changing any medically required concomitant medication known to be hepatotoxic to a suitable alternative. Table 10–2 summarizes the approach to investigate PDILI.

Table 10-2: Required investigations and follow up for PDILI

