12.4 Planned safety analyses

The long-term safety of BRV at individualized doses will be evaluated by means of the safety analyses. Summary tables will be presented over the Evaluation Period as well as Down-Titration Period for all subjects.

All safety variables will be analyzed by descriptive methods on the SS. Treatment-emergent adverse events will be summarized in incidence tables by Medical Dictionary for Regulatory Activities (MedDRA®) Primary System Organ Class and Preferred Term. Separate tables will be provided for AEs leading to withdrawal from the study and SAEs.

Laboratory values, vital signs, and weight will be summarized by period and visit. Possibly clinically significant treatment-emergent abnormalities for laboratory values, vital signs, and weight will be listed and summarized by period and visit. Electrocardiogram abnormalities will also be listed by period and visit.

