### **3.2.7        Last Value on BRV Treatment**

Last Value for clinical laboratory parameters, vital signs, and ECGs is the last available result obtained after the first dose of BRV and prior to or on the date of last dose of BRV. All scheduled and unscheduled assessments within this time period will be considered. Last Value will be determined separately for each laboratory parameter.

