#### **9.3.1.2 PDILI laboratory measurements**

The number and percentage of subjects with PDILI will be summarized in table by study group. In addition, the number and percentage of subjects meeting ALT or AST or both, total bilirubin and symptoms criteria will be summarized in table.

Listings of subjects with PDILI include alcohol use within past 6 months, the laboratory results for ALT, AST and Total bilirubin, symptoms of hepatitis or hypersensitivity, action and follow up will be provided only if any subject reporting PDILI.

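### The SAP plans no count of subjects with any laboratory PCST value on treatment, and leaves out the by-period PCST summary that protocol 12.4 promises

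*SAP*

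**What the plan says.** Protocol 12.4 commits to this: "Possibly clinically significant treatment-emergent abnormalities for laboratory values, vital signs, and weight will be listed and summarized by period and visit". The same section says that safety summaries will cover the Evaluation and Down-Titration Periods.

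SAP 9.3.1.1 states that PCST "abnormalities for laboratory values will be summarized by visit and at Last Value as stated above". The text above that sentence sets the time points: "for each scheduled visit (not including EV) and for Last Value". SAP 3.2.7 defines Last Value as "the last available result obtained after the first dose of BRV and prior to or on the date of last dose of BRV" and adds: "All scheduled and unscheduled assessments within this time period will be considered". SAP 9.3.1.1 then says: "The PCST abnormality will also be summarized with shift tables of post-baseline results versus baseline results".

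For potential drug-induced liver injury (PDILI), SAP 9.3.1.2 says: "The number and percentage of subjects with PDILI will be summarized in table by study group". Protocol 10.2.1 says: "All PDILI events must be reported as an AE".

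SAP 3.8, the place for departures from protocol-defined analyses, lists none.

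**The concern.** The primary objective is long-term safety. For a laboratory parameter, the basic long-term figure is how many subjects were ever abnormal on treatment. The plan gives a series of visit-specific proportions and one end-of-treatment proportion, and neither answers that question.

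Scheduled sampling is also sparse. After the first year a full panel is due only twice a year, so a short-lived abnormality may be seen only at an unscheduled draw. If it has resolved by the last on-treatment sample, the by-visit and Last Value tables will not show it. Whether the shift table shows it depends on a rule the SAP does not state.

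Separately, a summary promised in the protocol has dropped out of the SAP without being declared.

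**Working it through.** There is no sample size, power or error rate to reproduce, because the study is descriptive. The check is of the text, with one illustration.

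**1. What by-visit rows can and cannot give.** Let r_j be the number of subjects with a PCST value at scheduled visit j. The number ever abnormal at scheduled visits, E, is known only to satisfy

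max(r_j) ≤ E ≤ min(sum of r_j, number of subjects assessed).

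One subject abnormal at three visits and three subjects abnormal once each can both produce a single case in each of three rows. The range widens with the number of rows. Protocol Table 5–3 places full panels at W8, W24 and W48 in year one, then at two visits a year (W72 and W96 in year two). SAP 5.4 reports retention out to month 96. Eight years of that visit schedule give 3 + 7 × 2 = 17 full-panel visits, or 16 for N01379 subjects, who skip Visit 3. This gap exists even if no unscheduled test is ever done.

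**2. Where an unscheduled abnormal result can appear.**

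| Planned output | Takes unscheduled results? | Gives subjects ever abnormal? |
|---|---|---|
| PCST by visit (SAP 9.3.1.1) | No, rows are scheduled visits | No |
| PCST at Last Value (SAP 3.2.7) | Yes, if it is the last on-treatment result | No |
| PCST shift table (SAP 9.3.1.1) | Not stated | Depends on the undefined rule |
| PDILI table (SAP 9.3.1.2) | Not tied to a visit | Yes, but only for ALT/AST, bilirubin and symptom criteria |
| TEAE tables (SAP 9.2.2) | Yes, if reported as an adverse event | For events, not for PCST thresholds |

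The PCST criteria in SAP 12.1.1 also cover neutrophils, platelets, sodium, potassium, creatinine and others. None of these has a counterpart to the PDILI table.

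**3. Protocol against SAP.** Protocol 12.4 asks for PCST by period and by visit. SAP 9.3.1.1 has by visit and Last Value, and no period. Under SAP 3.2.5 the Down-Titration Period starts the day after the Early Discontinuation Visit and ends at the last dose, and the Final Visit follows the drug-free period. No scheduled visit falls inside Down-Titration, so by-visit rows cannot stand in for a Down-Titration summary.

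**4. Illustration of sampling coverage.** Assumptions, not taken from the documents: onset uniform over W0–W48, and duration d weeks. While the windows do not overlap, the share coinciding with a scheduled draw is (number of draws × d) / 48.

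| Scheduled draws | d = 1 | d = 2 | d = 4 | d = 8 |
|---|---|---|---|---|
| Full panel W8, W24, W48 | 6.3% | 12.5% | 25.0% | 50.0% |
| Full panel W24, W48 (N01379) | 4.2% | 8.3% | 16.7% | 33.3% |
| Liver tests W8, W12, W24, W36, W48 | 10.4% | 20.8% | 41.7% | 75.0% |

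Examples: 3 × 2/48 = 12.5%; 5 × 4/48 = 41.7%. For liver tests at d = 8, the W8 and W12 windows overlap by 4 weeks, so the share is (5 × 8 − 4)/48 = 75.0%. The panel at the End of Study or Early Discontinuation Visit is left out because its timing is not fixed.

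These figures describe how thin scheduled sampling is. They do not measure understatement.

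**The case against.** A reader might infer that unscheduled abnormalities enter no count at all and that the trial's safety result is therefore too low. The documents do not support this. Last Value expressly admits unscheduled results. The shift table is not restricted to scheduled visits, and an undefined rule is not an exclusion. PDILI subjects are counted whatever the visit, and PDILI events must be reported as adverse events. The primary safety variable is TEAEs, and an abnormal laboratory finding can be one, so any shortfall concerns the laboratory PCST tables and not the primary safety result.

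A reader might also take the complement of the coverage figures as the share of abnormalities missed. That does not follow. An abnormality that nobody samples is never measured, and an any-time count could not recover it. Mandatory repeat liver tests do not fill the gap with new subjects either: where the first result came from a scheduled sample at PCST level, that subject is already in the visit row.

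Three further points have some weight. Protocol 12.4 could be read as visits within periods, although the SAP states no such layout and Down-Titration contains no scheduled visit. The SAP's amendment history shows that a worst-value PCST summary was removed, which suggests choice and not oversight; that text is superseded, and its removal is not itself an error. An any-time proportion grows with exposure and with the number of draws, and subjects leave at different times. This last point stands as a caution on interpretation. It does not replace the missing count.

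**Conclusion.** The point holds in a limited form. The planned tables cannot yield the proportion of subjects ever meeting a laboratory PCST criterion. An abnormality found at an unscheduled test that resolves before the last on-treatment value is not assured of a place in any laboratory PCST table. The by-period PCST summary in protocol 12.4 has no counterpart in SAP 9.3.1.1, and SAP 3.8 does not declare this.

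The size of any understatement cannot be computed, since the documents give no rate of unscheduled tests or of PCST values. The coverage figures rest on assumed onset and duration and show only that scheduled sampling is sparse.

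The reading of protocol 12.4 uses the text supplied, which runs to Amendment 4. The SAP cites Amendment 4.1 and describes it as a Japan-specific change about continuing the study after approval, so section 12.4 is assumed unchanged.

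**What to change.** In SAP 9.3.1.1:

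- Add, per parameter, the number and percentage of subjects with at least one PCST value (low and high separately where both apply) over all scheduled and unscheduled assessments from first to last dose. Give it overall and for the Evaluation and Down-Titration Periods. The denominator is subjects with at least one post-baseline assessment.
- State that the shift table uses the worst on-treatment value, taken in each direction where a criterion has both.
- Keep the by-visit and Last Value tables.

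Reconcile SAP 9.3.1.1 and 3.8 with protocol 12.4: either restore the by-period summary or declare the change.

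The cost is a few SAP sentences and one extra table block, using data already collected. The any-time incidences will be at least as high as any by-visit count and will depend on exposure length and number of draws, so they should be presented beside the exposure summary in SAP 9.1.1.
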